6.6 Study Specific Procedures

Clinical Evaluations:

All primary endpoint assessments must be done by an Investigator who is a board-certified dermatologist.

6.6.1 Grading of signs and symptoms of TV

Each treated TV lesion will be evaluated for the following component signs and symptoms of the target TV lesion: Scaling, erythema, pruritus and dyspigmentation. Each component is measured using the following scale:

Scaling score:

0 None complete absence

1	Mild	slight
2	Moderate	definitely present

3 Severe marked, intense

Erythema score: (redness presents specifically in the target TV lesion)

0	None	No redness
1	Mild	Mildly detectable erythema; pink
2	Moderate	Dull red; clearly distinguishable
3	Severe	Deep, dark red; marked and extensive

Pruritus score: (itching; present specifically in the target TV lesion)

0	None	No itching
1	Mild	Occasional, slight itching
2	Moderate	Constant or intermittent itching; does not disturb sleep
3	Severe	Bothersome itching that disturbs sleep or normal activity

Dyspigmentation score: (Changes in color of the target TV lesion)

0	None	No change in color
1	Mild	Minor change in color
2	Moderate	Definite change in color
3	Severe	Marked change in color

To calculate the score, the component scores are added together.

6.6.2 Local Tolerability for Areas Affected by TV (application site reaction)

Local tolerability for anatomical locations to which the IP, aqueous gel and vehicle gel are applied will be evaluated based on these signs and symptoms:

Pain/Burning: as reported by the subject as being the greatest intensity they have experienced within the last 24 hours at Baseline or since the last visit at subsequent visits.

0	None	No pain/burning
1	Mild	Slight burning/stinging sensation; not really bothersome
2	Moderate	Definite warm, burning/stinging that is somewhat bothersome
3	Severe	Hot burning/stinging sensation that causes definite discomfort and
		may interrupt daily activities and/or sleep.

Pruritus: as reported by the subject as being the greatest intensity they have experienced within the last 24 hours at Baseline or since the last visit at subsequent visits.

0	None	No pruritus
1	Mild	Slight pruritus, not really bothersome
2	Moderate	Definite pruritus that is somewhat bothersome
3	Severe	Intense pruritus that may interrupt daily activities and/or sleep

Erythema: as assessed by the Investigator

0	None	No erythema present
1	Mild	Slight pink coloration
2	Moderate	Definite redness
3	Severe	Marked erythema, bright red to dusky dark red in color

Edema: as assessed by the Investigator

0	None	No edema
1	Mild	Slight, but definite edema
2	Moderate	Definite edema
3	Severe	Marked edema

Scabbing/Crusting: as assessed by the Investigator

0	None	No scabbing/crusting
1	Mild	Slight, but definite scabbing/crusting
2	Moderate	Definite scabbing/crusting
3	Severe	Marked scabbing/crusting

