This is a single center, randomized, double-blinded, vehicle and aqueous gel -controlled, within-patient, phase 2 comparison trial.

The trial includes a Screening and Enrollment period of up to 28 days, a 1-day or 5-day Treatment Period, and a Safety Follow-Up Period to Day 14.

Subjects meeting the inclusion/exclusion criteria at screening will be enrolled into one of four cohorts of the study. Each of the three DBI-002 probiotic cohorts will have two subjects enrolled to receive a single treatment dose, and four subjects enrolled to receive a once daily treatment dose for five consecutive days. The vehicle gel vs. aqueous gel cohort will have four subjects enrolled to receive a once daily treatment dose for five consecutive days.

Each subject will be randomly assigned to have the assigned dose of DBI-002 probiotic, vehicle gel, or aqueous gel applied to the TV-affected skin location (~100 cm²) on their chest or back. Neither the subject nor the evaluating Investigator will know to which treatment group each TV-affected skin location has been assigned.

Subjects enrolled to receive a single treatment dose will have study visits scheduled to occur on Day 0 for screening and enrollment, Day 1 baseline/treatment, and Day 5 and Day 14 (± 2 days) for follow-up. The screening and baseline/treatment visits may be combined if all eligibility criteria are met. There will be 3 or 4 study visits for subjects enrolled to receive a single treatment.

[figure not shown]
Subjects enrolled to receive a once daily treatment dose for five consecutive days will have study visits scheduled to occur at screening/baseline and on treatment period study days, Days 1, 2, 3, 4, and 5, and for a safety follow-up visit on Day 14 (± 2 days). The screening and baseline/treatment visits may be combined if all eligibility criteria are met. There will be 6 or 7 study visits for subjects enrolled to receive multiple treatments.

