For each of the three DBI-002 probiotic cohorts, the single-treatment subjects (approximately 2) will be enrolled first. After every single-treatment subject has completed the Day 5 visit, local tolerability and adverse events (AEs) will be assessed. If there are no safety signals, enrollment of the cohort's multiple treatment subjects (approximately 4) will begin. After every multiple treatment subject has completed the Day 14 visit, local tolerability and adverse events (AEs) will be assessed. If there are no safety signals, enrollment of the next cohort will begin. Cohort 1 must be completed before enrolling Cohort 2. Cohort 2 must be completed before enrolling Cohort 3. If there are safety signals specific to local tolerability and AEs from either of the first two cohorts, the following dose escalating cohort may be not be enrolled if the Investigator and sponsor are in agreement.

Cohort 4 subjects will receive multiple treatments, Enrollment of Cohort 4 is independent of the three probiotic cohorts.

Study Flowchart

Visit 0 (may be combined with Visit 1): Screening and enrollment visit, KOH test of TV-affected chest and back skin locations

Visit 1: Baseline visit, Urine pregnancy test as applicable, clinical grading of signs and symptoms of TV, randomization of IP or aqueous gel to chest and back, scrub samples and samples for bacterial culture of IP and vehicle gel TV-affected anatomical locations prior to applications, application of IP and vehicle gel, adverse event recording

Visit 2: Clinical grading of signs and symptoms of TV, scrub samples and samples for bacterial culture of IP and aqueous gel TV-affected anatomical locations, clinical assessment of local tolerability, adverse event recording

Visit 3: Final study visit. Urine pregnancy test as applicable, clinical grading of signs and symptoms of TV, KOH test of TV-affected chest and back skin locations, scrub samples and samples for bacterial culture of IP and aqueous gel TV-affected anatomical locations, adverse event recording, standard-of-care TV treatment may be provided at the discretion of the Investigator

Subjects enrolled to the multiple treatment dose groups:

Visit 0 (may be combined with Visit 1): Screening and enrollment visit, KOH test of TV-affected chest and back skin locations

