6.5 Study Visits

The study will be conducted with:

- 1. A screening visit (Day -28 to Day 1),
- 2. Baseline visit (Day 1) for evaluation, sampling and treatment may be combined with the screening visit
- 3. Only for subjects enrolled to receive multiple treatment doses: Treatment and evaluation visits (Days 2, 3, 4)
- 4. Evaluation and sampling visit (Day 5), and treatment only for subjects enrolled to receive multiple treatments
- 5. Safety follow-up visit (Day 14)

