6.5.2 All Other Visits

Study visit assessments will be conducted as presented in Appendix 1. The Treatment Period for subjects receiving a single treatment dose is Day/Visit 1. The Treatment Period for subjects receiving multiple treatment doses is from Day/Visit 1 through Day/Visit 5.

Day 1/Baseline visit (before the IP is applied, the following tasks will have been completed):

- 1. Review of Inclusion/Exclusion Criteria.
- 2. Ensure no direct use of soap and water for at least 12 hours on the areas where the samples are to be collected on the chest and back. After sampling and application, instruct the subject not to use soap and water on the chest and back until the morning of the next day.
- 3. Concomitant medications.
- 4. Clinical assessment of signs and symptoms of TV.
- 5. Score the signs and symptoms of local tolerability of the areas affected by TV.
- 6. Collect scrub samples from each of the TV-affected skin locations to be treated with IP, aqueous gel, and vehicle gel.
- 7. After collecting each scrub sample, pat the sampling location dry with wipes.
- 8. Collect samples for bacterial culture of the IP and vehicle gel TV-affected skin locations. Not required for vehicle gel vs. aqueous gel subjects.
- 9. Assigned IP, aqueous gel, and vehicle gel will then be applied to designated locations on both anterior and posterior trunk (chest or back) by investigative site staff. Approximately 0.1-0.2 ml of the IP, vehicle gel, or aqueous gel will be applied to each selected location.
- 10. Record any adverse events.
- 11. Schedule an appointment for Day 5 for subjects receiving a single treatment dose and instruct the subject to not use soap and water on the chest and back for at least 12 hours before the Day 5 visit. Schedule an appointment for the next day for the Day 2 visit for subjects receiving multiple treatment doses.
- 12. Instruct the subject to not wash the treated locations with soap and water on the anterior and posterior trunk (chest or back) from the time of IP, vehicle gel, and aqueous gel application at the Baseline visit until the morning of the next day.

For subjects enrolled to receive multiple treatment doses only:

Day 2 / Visit 2, Day 3 / Visit 3, Day 4 / Visit 4:

- 1. Clinical assessment of signs and symptoms of TV.
- 2. Score the signs and symptoms of local tolerability of the locations affected by TV.

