7.3 Analysis of Safety Data for Objectives

7.3.1 Local Tolerability

Signs and symptoms of local tolerability (pain / burning / stinging, pruritus, erythema, edema, and scabbing / crusting) will be summarized with changes from baseline.

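### Two tolerability items pair a 24-hour baseline with a since-last-visit worst score, so their change from baseline leans towards worsening at single-dose Day 5 and at Day 14

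*Combined protocol and SAP*

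**What the plan says.** Section 6.6.2 lists five local tolerability items, each graded 0 to 3. Pain/burning and pruritus are reported by the subject as the "greatest intensity they have experienced within the last 24 hours at Baseline or since the last visit at subsequent visits". The other three (erythema, edema, scabbing/crusting) are graded by the investigator with no look-back period, for example "Erythema: as assessed by the Investigator".

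The Synopsis (Study Design/Type) sets the visits. Single-dose subjects come on "Day 1 baseline/treatment, and Day 5 and Day 14 (± 2 days) for follow-up". Multiple-dose subjects come on "treatment period study days, Days 1, 2, 3, 4, and 5, and for a safety follow-up visit on Day 14 (± 2 days"). Section 6.5 confirms that the visits between Day 1 and Day 5 are "Only for subjects enrolled to receive multiple treatment doses: Treatment and evaluation visits (Days 2, 3, 4"). At those visits section 6.5.2 requires staff to "Score the signs and symptoms of local tolerability of the locations affected by TV", and it scores tolerability again on Days 5 and 14.

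The whole analysis in section 7.3.1 is that the items "will be summarized with changes from baseline". It names no contrast between the two treated sites and makes no allowance for window length.

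Tolerability belongs to the primary safety endpoint (section 4.2.1) and feeds two enrolment reviews. The Synopsis and section 4.1.1 say: "After every single-treatment subject has completed the Day 5 visit, local tolerability and adverse events (AEs) will be assessed", and a clean result opens the multiple-dose group of that cohort. A similar review after the multiple-dose subjects' Day 14 visits opens the next cohort.

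**The concern.** A worst score tends to rise with the length of the period it covers. Here the baseline covers one day and some later scores cover four or nine, so subtracting one from the other mixes any effect of the gel with the effect of a longer look-back. Background symptoms are plausible, at least for pruritus, because every subject has tinea versicolor and section 6.6.1 grades itching as one of its symptoms.

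Two readings are at risk. Change from baseline can suggest a reaction where none occurred. And a Day 5 display of single-dose beside multiple-dose subjects sets a four-day maximum beside a one-day maximum. The affected visits, single-dose Day 5 and multiple-dose Day 14, are the ones used for the enrolment reviews. Those rest on about two and four subjects per cohort, with no numerical definition of a safety signal.

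**Working it through.** **Recall windows, from the visit days**

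| Score | Single dose | Multiple dose |
|---|---|---|
| Baseline | 1 day (24 h) | 1 day (24 h) |
| Days 2, 3, 4 | no visit | about 1 day each |
| Day 5 | 5 − 1 = 4 days | 5 − 4 = 1 day |
| Day 14 (±2) | 14 − 5 = 9 days (12 − 5 = 7 to 16 − 5 = 11) | same |

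**Subjects affected.** Single dose: 3 × 2 = 6. Multiple dose: 3 × 4 + 4 = 16. Total 22, as planned. The four-day window concerns the 6; the Day 14 window concerns all 22.

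**No figure to reproduce.** The documents give no symptom rate, SD or day-to-day correlation. The rates and correlations below are assumptions.

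**Any symptom in the window, no treatment effect, independent days.** With daily chance p and k days, the probability is 1 − (1 − p)^k.

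| p | k = 1 | k = 4 | k = 9 |
|---|---|---|---|
| 5% | 5% | 18.5% | 37.0% |
| 10% | 10% | 34.4% | 61.3% |
| 20% | 20% | 59.0% | 86.6% |

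**Mean bias on the 0–3 scale, independent days.** The expected maximum over k days is the sum, over grades 1 to 3, of the chance that the maximum reaches that grade. Take daily probabilities 0.90, 0.07, 0.02 and 0.01 for grades 0 to 3 (10% symptomatic days):

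- k = 1: 0.10 + 0.03 + 0.01 = 0.14
- k = 4: (1 − 0.90^4) + (1 − 0.97^4) + (1 − 0.99^4) = 0.344 + 0.115 + 0.039 = 0.498
- k = 9: (1 − 0.90^9) + (1 − 0.97^9) + (1 − 0.99^9) = 0.613 + 0.240 + 0.086 = 0.939

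Bias is 0.498 − 0.14 = +0.36 at single-dose Day 5, 0.939 − 0.14 = +0.80 at Day 14, and 0 at multiple-dose Day 5.

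**Effect of day-to-day correlation.** Symptoms usually persist, so independence is the high end. A simulation of 200,000 subjects with no treatment effect and no time trend used a latent daily score with AR(1) or exchangeable correlation. Mean change from baseline with 10% symptomatic days:

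| Correlation | Multiple-dose Day 5 | Single-dose Day 5 | Day 14 |
|---|---|---|---|
| 0 | 0.00 | +0.36 | +0.80 |
| 0.5 (AR(1) / exchangeable) | 0.00 | +0.28 / +0.24 | +0.64 / +0.46 |
| 0.8 (AR(1) / exchangeable) | 0.00 | +0.17 / +0.15 | +0.40 / +0.25 |
| 0.95 (AR(1) / exchangeable) | 0.00 | +0.08 / +0.07 | +0.18 / +0.11 |

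With 30% symptomatic days (0.70, 0.20, 0.08, 0.02), the same formula for independent days gives +0.76 at single-dose Day 5 and +1.32 at Day 14. At exchangeable correlation 0.95 the simulation gives +0.14 and +0.21. In the limit of constant daily symptoms, every window returns the same score and the bias is zero.

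**Check of the remedy.** At any one visit the two sites of a subject share the same window. If both follow the same symptom process, each carries the same expected shift, and the difference between sites has expectation zero. In multiple-dose subjects the maximum of the Day 2, 3, 4 and 5 scores covers 1 + 1 + 1 + 1 = 4 days, the same period as the single-dose Day 5 score.

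**The case against.** The strongest defence is that a worst score since the last visit is the right way to collect safety data. Single-dose subjects are not seen on Days 2 to 4, and a reaction on Day 2 would otherwise be lost. That stands. The weakness is only in subtracting a 24-hour baseline from that score.

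The scope is also limited. Three of the five items have no recall window, and multiple-dose scores on Days 2 to 5 already match the baseline window. The background-symptom argument is stronger for pruritus than for pain/burning, which is not a graded sign of the disease. Each subject has an aqueous gel site scored over the same window, so the data for a protected contrast are already collected. All of this stands, but section 7.3.1 does not ask for that contrast.

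Some stronger readings are tempting and do not hold:

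- A reader might infer that every later score must equal or exceed baseline. It need not: the later windows begin after the baseline 24 hours and do not contain them. The bias is an average tendency, and real improvement could mask it.
- A reader might take the independent-day percentages at p = 10% as expected rises of about 24 points (34.4 − 10) and 51 points (61.3 − 10). They rest on an assumed rate and on days with no persistence.
- A reader might infer that a planned comparison of regimens is invalid, or that an enrolment review will go wrong. Sections 7.1 to 7.3 plan no such tolerability test. The reviews ask about safety signals without a change-from-baseline threshold, and the stopping rule in section 6.4.3 refers to Grade 3 or higher related adverse events.
- A reader might conclude that a 24-hour score should replace the worst score. At Day 5 it would cover 72 to 96 hours after the only application in single-dose subjects, but the first 24 hours after the Day 4 application in multiple-dose subjects. The regimens would still not be comparable, and early single-dose reactions would drop out.

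**Conclusion.** The point holds in limited form. For pain/burning and pruritus, the change from baseline in section 7.3.1 is biased on average towards worsening at single-dose Day 5 and at Day 14 whenever symptoms fluctuate, and Day 5 summaries of the two regimens rest on four-day and one-day windows. The windows follow directly from sections 6.6.2 and 6.5 and the Synopsis.

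The size does not follow from the documents. Under the assumed 10% of symptomatic days it ranges from +0.07 to +0.36 at single-dose Day 5 and from +0.11 to +0.80 at Day 14, assuming no treatment effect, no time trend and correlation between 0 and 0.95. The documents do not support a claim that tolerability as a whole is compromised. This is an inexpensive analysis improvement in a descriptive study, worth making because these items belong to the primary safety endpoint and inform the enrolment reviews.

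**What to change.** 1. **Section 6.6.2:** keep the worst-since-last-visit score for safety capture.
2. **Section 7.3.1:** for pain/burning and pruritus, make the main summary the within-subject difference, IP site (or vehicle site in Cohort 4) minus aqueous gel site, at each visit and for change from baseline. Continue to show each site's own scores, because a reaction common to both gels cancels in the difference. State the recall window beside each visit.
3. **Enrolment reviews:** provide this within-subject summary at the Day 5 and Day 14 reviews, in a form that protects the blind of the evaluating investigator.
4. **Side-by-side Day 5 displays:** for multiple-dose subjects use the maximum of the Day 2 to Day 5 scores, so that both regimens cover Day 1 to Day 5. Its change from baseline still carries the four-day bias, so read it with the site difference.
5. **Optional:** add a 24-hour score at Days 5 and 14 as a supplementary item for a like-for-like change from baseline, not as a replacement. This must be decided before data collection, because the score cannot be recovered afterwards.

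Cost: slightly more analysis work and a wording change in section 7.3.1. Items 1 to 4 need no new data. The optional item adds two short questions per site and a small change to section 6.6.2 and the case report form.

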6.6.3 Sample Collection

One representative anatomic location (chest or back), according to the grading of signs and symptoms of TV, must be classified as at least moderate to be designated as the Active Sampling (or target lesion) location on both anterior and posterior trunk (chest or back).

Subjects with both target areas affected, will have samples collected from both chest and back. One anatomical location on either chest or back will be designated as treatment site and other site as control.

KOH test will be done at the investigative site.

Scrub samples will be sent to the sponsor

The subject's cultures will be sent to the local

microbiology laboratory.

An informational grid for sample collection and processing required for the study is shown in Table 3 below.

Table 3. Microbiological Samples.

Visit	KOH testing at the investigative site	Scrub samples for molecular diagnostics	Collect samples for bacterial culture		
Screening	Target lesion on both chest and back				
Day 1 (Baseline - Prior to dose)		Target lesion on both chest and back	Target lesion on both chest and back		
Day 5		Target lesion on both chest and back	Target lesion on both chest and back		
Day 14 Target lesion on both chest and back		Target lesion on both chest and back	Target lesion on both chest and back		

 Δ Not applicable for Cohort 4 subjects

Throughout the study, continuous monitoring of concomitant medications, therapies and AEs will occur.

6.7 Test Article (IP, vehicle gel, aqueous gel) Administration

Subjects will have either a Day 1 single treatment dose or 5 daily treatment doses (Day 1 to Day 5) of their assigned test articles (IP, vehicle gel, aqueous gel) applied by study personnel at the investigative site during the Treatment Period. Details of test article preparation will be provided in the Pharmacy Manual. Approximately 0.1 ml of the IP and vehicle gel will be applied to TV designated locations (each 100 cm²) on treatment and control skin lesions, respectively. The test article will be allowed to air dry.

6.8 Concomitant Medication

Usage of prescription or over the counter topical or systemic medications will be reported during the subject's participation in the study. At the screening visit, the use of anti-fungal or antibacterial treatments in the past 4 weeks is an exclusion criterion.

6.9 Investigational Product

The IP, vehicle gel, or aqueous gel will be applied by study personnel at the investigative site at the baseline/Day 1 visit only for subjects receiving a single treatment dose, and once daily for 5

applications during the study for subjects receiving multiple treatment doses. Approximately 0.1 of the IP will be applied to a 100 cm² area of the TV-affected skin on the chest or back. The control location will be treated with 0.1ml of vehicle gel.

The doses for the three probiotic IP cohorts are 10^6 CFU/ ml, 10^8 CFU /ml, and 10^{10} CFU/ ml vs. vehicle gel.

It has been estimated that the density of bacteria on normal skin is approximately $1 \ge 10^{5}$ /cm². At our highest dose of 10^{10} CFU/ ml applying 0.1 ml to each 100 sq.cm. site will be adding $1 \ge 10^{10}$ CFU/cm² on chest or back.

The doses in this trial are comparable to the doses used in the study of other topical live bacterial products. An ammonia oxidizing bacterium has been used in Phase 2 trials to treat acne at a dose of 10^9 CFUs/ml (Whitlock 2017). In addition, a coagulase-negative *Staphylococcus* strain at a dose of $10^{7/}$ ml CFUs (Williams & Gallo, 2015) has been used in atopic dermatitis patients, and a strain of *P. acne* has been applied to the face of acne patients at a dose of $10^{8/}$ ml CFUs (NCT03450369).

Detailed information of the IP is included in the Investigator's Brochure (IB), provided separately.

